4.4.3 Other Laboratory Tests

- Post-menopausal determination at Visit 1 (screening): Follicle stimulation hormone (FSH) in female patients.
- Urine Drug Screen measured at screening and Visit 1 (Screening): Amphetamine, Benzodiazepines, THC, Cocaine, Oxycodone and Opiate.
- PTH (parathyroid hormone)

4.4.4 Vital Signs

Vital signs (body temperature, heart rate, blood pressure, oxygen saturation) will be performed at all clinic visits prior to IMP dosing: Visit 1 (screening), Visit 2 (Week 1), Visit 3 (Week 4), Visit 4 (Week 14), Visit 5 (Week 26), Visit 6 (Week 30), safety follow up. All assessments will be collected in the supine position.

Weight will be measured at visit 1 (screening).

4.4.5 Electrocardiograms

A 12-lead ECG will be performed at all clinic visits. 12-lead serial ECGs will be recorded at visit 2 (enrolment) pre-dosing and after 30 minutes, 1 hour and 2 hours post-dosing (\pm 10 minutes).

The clinical significance of ECG results will be determined by the investigator after review of the ECG report in relation to the patient's medical history, physical examination findings, and concomitant medications.

4.4.6 Physical Examination

A standard complete physical examination will be performed at Visit 1 (Screening), Visit 2 (Enrolment), Visit 3, Visit 4 and Visit 5.

PAREXEL International Statistical Analysis Plan

Medivir
Protocol: MIV-711-202

Final 1.0
16 January 2018

4.4.7 Prior and Concomitant Medications

All prior and concomitant medications taken during the MIV-711-202 study will be recorded with generic name, indication, daily dose, and start and stop dates of administration at each visit. For this study, prescription medicines, other than those prohibited by the study protocol are permitted as concomitant medications to manage ongoing or chronic, stable medical conditions. Concomitant medications from the MIV-711-201 study that were taken prior to visit 2 in the MIV-711-202 study are captured as prior medications in the current study. Any change in prior medications past visit 2 IMP administration in MIV-711-202, or any new medications, are documented as concomitant medication. All patients will be asked about concomitant medication use and any changes to use of concomitant medications at all study visits. Patients will be permitted to reinstate prohibited concomitant medications on completion of their follow up study visit.

The Brief Medication Questionnaire self-reported measure for the use of concomitant medication will be included at visit 4 and visit 5.

4.4.8 Phone Call to Assess Safety and Tolerability

Follow-up telephone calls to assess safety and tolerability will occur 5 to 9 days after visit 2, visit 3 and visit 4. There will be additional phone calls at Week 10 and Week 20 for safety and tolerability.

4.5 Efficacy Variables

4.5.1 MRI Bone Shape Modelling by Imorphics

MRIs will be analysed quantitatively using statistical shape modelling (SSM, Imorphics Ltd).

Bone shape modelling of MRI by Imorphics will be used to assess:

- Mean cartilage thickness (mm) for each of the anterior, posterior and central regions, with areas denuded of cartilage included as having zero thickness
- Bone marrow lesion volume (mm³) by anatomical region: medial and lateral femorotibial region of femur, medial and lateral patellofemoral region of femur, medial and lateral tibia, and patella
- Bone area (mm²) for anatomical regions: lateral and medial femur (patellofemoral); lateral and medial femur (femorotibial); lateral and medial patella, lateral and medial tibial condyle
- Bone shape by distance along an OA shape vector for femur, tibia and patella
- Index bone area/cartilage thickness

PAREXEL International Statistical Analysis Plan

Medivir
Protocol: MIV-711-202

Final 1.0
16 January 2018

Below are the denominations of the data items provided by Imorphics that will provide the basis for bone area and cartilage thickness and bone marrow lesion volume.

- MF_TAB: Area of bone in the medial femur region, MF
- CM_FEMUR_THCTAB: Average thickness of cartilage in the central medial femur region
- CM_TIBIA_THCTAB: Average thickness of cartilage in the central medial tibia region
- TOTAL_BML_VOLUME: Combined volume of all BML regions

4.5.2 MRI MOAKS

MRIs will be analysed semi-quantitatively by a central musculoskeletal radiologist using the MOAKS.

MOAKS scoring will be used to assess the following features:

- Bone marrow lesions (BMLs) and cysts
- Articular cartilage
- Osteophytes

MRI assessment using MOAKS scoring will be used to assess the following features, as provided by PAREXEL MRI:

- Bone Marrow Lesions (BMLs) and cysts. This involves 15 subregions graded for BML size (including ill-defined lesion and cysts) measuring the total volume of the subregion occupied by BML(s). Grade 0= none, grade 1 < 33% of subregional volume, grade 2 = 33 to 66% of subregional volume and grade 3 > 66% of subregional volume.
- Articular Cartilage: This involves 14 articular cartilage regions graded for size of any cartilage loss (including partial and full thickness loss) as a percentage of surface area as related to the size of each individual region surface and percentage of loss in this subregion that is full-thickness loss.
- Osteophytes: This involves 12 sites scored for presence and size of osteophytes. Grade 0=none, Grade 1= small, Grade 2 = medium, Grade 3 = large.

The specific subregions associated with the above three groups of MOAKS scoring are outlined in the table below:

Bone Marrow Lesions (BMLs) and cysts	Articular Cartilage	Osteophytes
Medial Patella	Medial Patella	Superior Patella
Lateral Patella	Lateral Patella	Inferior Patella
Medial Femur Trochlea	Medial Femur Trochlea	Medial Patella

PAREXEL International Statistical Analysis Plan

Medivir
Protocol: MIV-711-202

Final 1.0
16 January 2018

Medial Femur Central	Medial Femur Central	Lateral Patella
Medial Femur Posterior	Medial Femur Posterior	Medial Femur Trochlea
Lateral Femur Trochlea	Lateral Femur Trochlea	Medial Femur Central
Lateral Femur Central	Lateral Femur Central	Medial Femur Posterior
Lateral Femur Posterior	Lateral Femur Posterior	Lateral Femur Trochlea
Medial Tibia Anterior	Medial Tibia Anterior	Lateral Femur Central
Medial Tibia Central	Medial Tibia Central	Lateral Femur Posterior
Medial Tibia Posterior	Medial Tibia Posterior	Tibia Medial
Subspinous	Lateral Tibia Anterior	Tibia Lateral
Lateral Tibia Anterior	Lateral Tibia Central	
Lateral Tibia Central	Lateral Tibia Posterior	
Lateral Tibia Posterior		

Bone Marrow Lesions (BMLs) and cysts: The 15 subregions will be assessed for:

- Size of BML
- Number of BMLs
- Percentage that is BML

Articular Cartilage: The 14 subregions will be assessed for:

- Size of any cartilage loss
- Percentage of Full Thickness Loss

4.5.3 Patient Reported Outcomes (PROs)

At Visit 4 and 5 the following PROs will be recorded using questionnaires as specified in the schedule of assessments (see Protocol Table 2).

- Average overall knee pain severity in the target knee over the past 1 week (0-10 NRS)
- Worst knee pain severity in the target knee over the past 1 week (0-10 NRS)
- Global disease activity over the past 1 week (0-10 NRS)
- Average overall knee pain severity in the contralateral knee over the past 1 week (0-10 NRS)
- Western Ontario and McMaster Universities Osteoarthritis Index (WOMAC)
Higher scores indicate worse pain, stiffness and physical function. The subscale scores are derived by summing the assigned values on component items. The study joint referred in the WOMAC questionnaire corresponds to the target knee (as referenced elsewhere in this protocol).
- Osteoarthritis Research Society International (OARSI)-OMERACT Responder index will be calculated using the WOMAC pain and function subscales and the patient's global assessment score.

PAREXEL International Statistical Analysis Plan

Medivir
Protocol: MIV-711-202

Final 1.0
16 January 2018

- Intermittent and constant osteoarthritis pain (ICOAP) - an 11-item tool designed to assess constant and intermittent OA pain. The tool will be self-reported. (The tool was designed for telephone or interview administration but self-reporting is allowed.) The questions will be scored according to a user manual into a constant pain subscale, intermittent pain subscale and total pain score. These scores will be transformed to a 0-100 scale for analysis.
- Global improvements in knee problem, knee pain and knee function recorded on a 6-point Likert scale: completely better, much better, better, no change, worse, much worse.
- EuroQol-5 Dimensions (EQ-5D-5L) (Visit 5 only) - a generic measure of self-reported health status that defines health status in terms of five dimensions – mobility; self-care; usual activity; pain or discomfort; and anxiety or depression
- In an e-diary format, a patient knee pain diary (NRS) and analgesia questionnaire will be completed daily during two 2-week periods prior to Visit 4 and Visit 5. Baseline (Visit 8 of Study MIV-711-201) will be defined as the last observation prior to the first dose of investigational product. The assessments in the e-diary comprise:
 - 1) Average overall knee pain severity in the target knee over the past 12 hours (0-10 NRS)
 - 2) Adherence to usual analgesics regimen
- Intake of IMP (only included with an attempt to improve compliance, no data to be reported)

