- Global improvements in knee problem, knee pain and knee function recorded on a 6-point likert scale: completely better, much better, better, no change, worse, much worse.
- EuroQol-5 Dimensions (EQ-5D-5L) [44] (Visit 5 only) - a generic measure of self-reported health status that defines health status in terms of five dimensions – mobility; self-care; usual activity; pain or discomfort; and anxiety or depression [45]. EQ-5D-5L has been extensively validated and shown to be sensitive, internally consistent, and reliable in the general population and other patient groups, including for inflammatory arthritis.[46]

- In an e-diary format, a patient knee pain diary (NRS) and analgesia questionnaire will be completed daily during two 2-week periods prior to Visit 4 and Visit 5. Baseline (Visit 2 of Study MIV-711-201) will be defined as the last observation prior to the first dose of investigational product. The assessments in the e-diary comprise.
  - 1) Average overall knee pain severity in the target knee over the past 12 h (0-10 NRS)
  - 2) Worst knee pain severity in the target knee over the past 12 h (0-10 NRS)
  - 3) Adherence to usual analgesics regimen
  - 4) Intake of IMP

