#### *9.5.3.1 Definition of Baseline for Exploratory Endpoints*

For the efficacy parameters, for Study Population A, changes from Baseline will be assessed using the Visit 2 baseline data from MIV-711-201. For Study Population B, changes from Baseline will be assessed using the Visit 8 data from Study MIV-711-201 which is expected to occur on the same calendar day as Visit 1 in Study MIV-711-202. For the biomarkers in Study Population B, the baseline will be Visit 2 in the present study (MIV-711-202).

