4.6.3 Safety Analysis Population (SAF)

The safety analysis population will be the same as the ITT population.

5. Protocol Deviations

Deviations from the protocol including violations of inclusion/exclusion criteria will be assessed as “minor” or “major” in cooperation with the sponsor. Major deviations from the protocol will lead to the exclusion of a patient from the Per Protocol Set (PPS). Deviations will be defined prior to data base hard lock.

The following criteria will be used to exclude a patient from an analysis set:

- Incorrect diagnosis
- Any of the prohibited interventions/injuries for the target knee
- Missing more than 7 doses of MIV-711
- Discontinuation from the study

Note: this is not an exhaustive list of deviations, these are only the deviations specified per protocol. The discussion during the data review meeting post data base soft lock will review all deviations collected at each site and it will be decided to which analysis set each patient belongs.

6. General Considerations for Data Presentations

In this study IMP refers to any amount of the treatments defined in section 3.5, regardless of the time or period of administration.

Data for all patients enrolled in study MIV-711-202 who receives at least one dose of IMP will be presented in the data listings.

PAREXEL International Statistical Analysis Plan

Medivir
Protocol: MIV-711-202

Final 1.0
16 January 2018

A patient who is enrolled in study MIV-711-202 but does not receive IMP will be included in those data listings for which they have data but will be excluded from all data summaries. Data summaries will only include those patients that receive IMP.

For those listings or data summaries where baseline and change from baseline measurements will be presented, unless stated otherwise, the baseline assessment to be used for calculating change from baseline will be the last valid assessment prior to first dose of 200 mg MIV-711. Note that the change from baseline will be calculated also for visits prior to the baseline visit, not only for visits succeeding the baseline visit.

Data from both studies for patients enrolled in study MIV-711-202 will be included in the data listings, tables and figures, as appropriate.

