7.9 Dose Administration

Information collected per the dose administration CRF will be listed including patient number, visit, date and time of administration, number of capsules dispensed and number of capsules returned.

The number and percentage of patients who received IMP will be summarized for each on site visit. Descriptive statistics will be used to summarize drug accountability as the number of capsules returned for each on site study visit by treatment.

Compliance will be derived as the number of days patient were exposed to IMP. 100% compliance will be considered for dosing during the period Visit 2 to Visit 5. The number of capsules used will be derived as the number of capsules dispensed minus the number of capsules returned. Subjects with less than 100% compliance will be identified among those who have results for “Reason not all unused Capsules returned”. The compliance will not be calculated for withdrawn patients, as the date of the last IMP dose taken is not captured in the database.

8. Pharmacodynamic Analysis – Efficacy

The baseline will be the last valid assessment prior to first dose of 200 mg MIV-711, i.e. the baseline visit is defined as

- Visit 2 in study MIV-711-201 for study group A
- Visit 8 in study MIV-711-201 for study group B

The exception is for the biomarkers in study group B, where the baseline visit is defined as visit 2 in the present study (MIV-711-202).

The change from baseline for visit X will be calculated as the (visit X – baseline visit) difference in observed values. Note that the change from baseline will be calculated for all visits in study MIV-711-201 and study MIV-711-202 where the actual endpoint has

PAREXEL International Statistical Analysis Plan

Medivir
Protocol: MIV-711-202

Final 1.0
16 January 2018

been observed, i.e. not only for visits in study MIV-711-202 succeeding the baseline visit.

All efficacy analyses will be made on the ITT population if not stated otherwise.

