8.3.7.1 Derived e-diary variables

Three e-diary variables will be derived:

- NRS score
- Percentage score for analgesic usage last 12 hours
- Severity and extent of their pain medication usage

For each e-diary endpoint and visit, a patient's summary value will be calculated by using the e-diary assessments recorded at the study days associated with that study visit. The study days associated with study Visit 'x' will be identified as follows: beginning at the last date of assessment associated with Visit 'x' and including up to 14 days prior to the visit recorded within 19 calendar days prior to the date of Visit 'x'. If there are less than 10 days of recorded e-diary assessment within those 19 calendar days, the summary value will not be calculated for that visit.

NRS score

The derived summary scores for e-diary NRS scores associated with each visit will be obtained as the arithmetic mean (the average) of all e-diary NRS scores observed during the study days associated with that visit (as defined above). Separate e-diary NRS summary scores will be provided for AM and PM response. In addition, the overall 24 hour summary score will be calculated as the mean of the AM and PM summary scores for each visit. The overall 24 hour summary score will only be calculated if both mean AM and mean PM scores are available.

Percentage score for analgesic usage last 12 hours

Each patient's 'pain medication usage over the last 12 hours (Yes/No)' will be calculated as the percentages of days with a YES-response of the study days associated with that visit (as defined above). This will provide each patient with a percentage score for analgesic use for each study visit and for each of AM, PM. The denominator for AM and PM percentage calculations will be the actual number of days assessed, such that the number of days is at least 10 days and less than or equal to 14 days. The overall percentage, combining AM and PM measures, will be calculated as the mean of the AM and PM percentages:

- Overall percentage = $(xx/AM \text{ denominator} + yy/PM \text{ denominator})/2$
where 'xx' is the count of AM 'Yes' responses, 'yy' is the count of PM 'Yes' responses.

PAREXEL International Statistical Analysis Plan

Medivir
Protocol: MIV-711-202

Final 1.0
16 January 2018

Severity and extent of their pain medication usage

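### The SAP gives three conflicting e-diary baselines; two of them would distort a descriptive change score, one in Group A and the other in Group B

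*SAP*

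**What the plan says.** The e-diary baseline is defined in several places.

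- Protocol 7.4.1, written for Study Population A: "Baseline (Visit 2 of Study MIV-711-201) will be defined as the last observation prior to the first dose of investigational product".
- Protocol 9.5.3.1, on exploratory endpoints: "For the efficacy parameters, for Study Population A, changes from Baseline will be assessed using the Visit 2 baseline data from MIV-711-201". For Population B it uses Visit 8 of Study 201, with a separate rule for biomarkers.
- SAP 4.5.3 repeats the sentence from protocol 7.4.1 with a different visit and for all patients: "Baseline (Visit 8 of Study MIV-711-201) will be defined as the last observation prior to the first dose of investigational product".
- SAP Section 6 gives the general rule, which applies unless something else is stated: "the baseline assessment to be used for calculating change from baseline will be the last valid assessment prior to first dose of 200 mg MIV-711".
- SAP Section 8 sets the efficacy baselines by group: "Visit 2 in study MIV-711-201 for study group A" and "Visit 8 in study MIV-711-201 for study group B". It names one departure: "The exception is for the biomarkers in study group B, where the baseline visit is defined as visit 2 in the present study". The e-diary is not excepted.
- Listing 16.2.6.22 (derived e-diary results) repeats the Section 8 split.
- The footnotes of Table 14.2.6.1 (e-diary pain) and of the analgesic-use table give Visit 2 of Study 201 for both groups. The analgesic-use table is 14.2.6.3, although its continuation page is numbered 14.2.6.4.

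On the value itself, SAP 8.3.7.1 derives one summary per e-diary endpoint and visit. For pain it is "the arithmetic mean (the average) of all e-diary NRS scores observed during the study days associated with that visit", calculated only when at least 10 diary days are recorded. SAP 8.3.7 takes change from baseline on these summaries.

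**The concern.** SAP 4.5.3 is the only SAP text written specifically about the e-diary baseline, and for Group A it names a visit that cannot be a baseline. Group A received 200 mg throughout Study 201, and Visit 8 is that study's 26-week end-of-treatment visit. It precedes the first dose of Study 202 but not the first dose of MIV-711. The SAP announces one discrepancy with the protocol, on analysis populations (4.6), but not this change of visit.

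The table footnotes fail in the other direction. Group B took placebo up to Visit 8 of Study 201, and its exploratory objective concerns the following 26 weeks on drug. A change counted from Visit 2 of Study 201 mixes the two periods.

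The same diary data could therefore yield different change scores according to which part of the SAP is programmed, and outputs for one endpoint could disagree with each other.

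**Working it through.** The documents state no figure for this point, so the check is a comparison of definitions followed by an identity. V2 and V8 below are visits of Study 201.

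| Source | Group A | Group B |
|---|---|---|
| Protocol 7.4.1 (Population A) | V2 | no separate baseline given |
| Protocol 9.5.3.1 | V2 | V8 |
| SAP 4.5.3 | **V8** | V8 |
| SAP 6, applied to the diary schedule | V2 | V8 |
| SAP 8 | V2 | V8 |
| Listing 16.2.6.22 | V2 | V8 |
| Footnotes, Tables 14.2.6.1 and 14.2.6.3 | V2 | **V2** |

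The SAP 6 row follows from the schedules. Study 201 has two-week diary periods before V2, V6 and V8; Study 202 has them before Visits 4 and 5 only. The last diary period before the first 200 mg dose is thus the one before V2 in Group A and the one before V8 in Group B.

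**Size of the discrepancy.** Let D2, D8 and D52 be a group's mean diary summary at V2, at V8 and at Visit 5 of Study 202, for the same patients. Then

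(D52 − D2) = (D52 − D8) + (D8 − D2).

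The two baselines differ by exactly D8 − D2, the mean change during Study 201. The documents give no value for it, so these are illustrations under assumptions.

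- *Group A.* Assume diary pain falls 1.0 point by week 26 and stays there: D8 − D2 = −1.0 and D52 − D8 = 0.0. SAP 8 reports −1.0 + 0.0 = −1.0; SAP 4.5.3 reports 0.0.
- *Group B.* Entry requires a rise of at least 2 on the clinic NRS during placebo. Assume the diary mean rises by 2.0. With no further change on drug, SAP 8 reports 0.0 and the footnotes report 0.0 + 2.0 = +2.0. With a 1.0-point fall on drug, SAP 8 reports −1.0 and the footnotes report −1.0 + 2.0 = +1.0, so the sign reverses.
- If D8 − D2 is zero in a group, the baselines agree for that group.

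**Reach.** SAP 8.3.7.2 sends the e-diary NRS score to the 8.1.1 mixed model. That model uses the observed score as response and has no baseline-score covariate. Its only baseline term is analgesic use, taken from concomitant medication. It estimates change from V2 in both groups, so the definition in 4.5.3 does not enter. What remains is descriptive: Tables 14.2.6.1 and 14.2.6.3 and Listing 16.2.6.22.

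**Shell layout.** Both tables leave the Change column blank for Group A at V2 and fill it for Group B at V2. Table 14.2.6.3 also leaves it blank for Group B at V8. That fits SAP 8 better than the tables' own footnotes, under which the Group B change at V2 would be zero by construction.

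**The case against.** The case for treating this as editorial is strong in several respects.

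- SAP 4.5.3 describes variables; Section 8 is the analysis rule, splits by group and does not except the e-diary. The phrase in 4.5.3 about preceding the first dose itself points to Visit 2 for Group A.
- Every e-diary change shell already gives Group A Visit 2 of Study 201, so programmers working from the shells would get Group A right. The conflict that actually reaches the outputs is in Group B.
- Observed values at the Study 201 visits are also tabulated, so the first 26 weeks remain visible.
- The endpoints are exploratory, and the protocol says the study is not powered for any confirmatory analysis.

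All of this stands and limits the consequence. It does not settle which definition governs: Section 6 yields to more specific statements, and 4.5.3 is the one specific to the e-diary. Nor does it answer the Group B footnotes.

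A reader might also infer from 4.5.3 that a single diary entry serves as baseline and is compared with means over 10 to 14 days. The documents do not support that. SAP 8.3.7 takes change on the derived summaries, 8.3.7.1 derives one for each visit, and Listing 16.2.6.22 carries Baseline as a row of derived results, with a note that the NRS value is the mean over the visit's interval. Section 8 uses a parallel phrase about the last valid assessment and goes on at once to name the baseline visit. The wording in 4.5.3 is loose, but it does not establish a single-entry baseline.

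**Conclusion.** The inconsistency is real and should be corrected: there are three e-diary baseline rules in one SAP. The split in SAP Section 8 matches protocol 9.5.3.1 and the general rule in SAP 6. SAP 4.5.3 departs from it for Group A, and the footnotes of the two change tables depart from it for Group B.

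The error from using the wrong rule is the group's mean change in the diary summary during Study 201. The figures of 1.0 and 2.0 points are assumptions; the Group B figure also assumes that diary pain tracks the clinic NRS used for entry.

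A reader might conclude that the plan discards Group A's first 26 weeks from its 52-week assessment. That goes too far. Visit 8 for Group A is one of several conflicting statements and not the settled rule, no e-diary shell uses it for Group A, and the mixed model is unaffected. The consequence is confined to exploratory descriptive change scores and one listing.

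**What to change.** Replace the baseline sentence in SAP 4.5.3 with: *E-diary baseline is the 8.3.7.1 visit summary for Visit 2 of Study 201 in Group A and for Visit 8 of Study 201 in Group B.* This resolves the visit and also removes the loose reference to a last observation.

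Correct the footnotes of Tables 14.2.6.1 and 14.2.6.3 to the same definition, and leave Change blank for Group B at Visit 8 of Study 201 in Table 14.2.6.1, as Table 14.2.6.3 already does. Listing 16.2.6.22 needs no change. Table 14.2.6.2 can keep Visit 2 of Study 201 as its reference visit, because that is what the model reports.

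The cost is one sentence, two footnotes and one shell cell block. Study 201 scheduled a two-week diary before both visits, so nothing further has to be collected and the model does not change.
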